12.5.3 Safety endpoints

For all safety analyses, the Safety set will be used.

Adverse events

All information obtained on AEs will be displayed by participant.

The number and percentage of participants with treatment emergent AEs (events started after the first dose of study medication or events present prior to start of study treatment but increased in severity based on preferred term) will be summarized in the following ways:

- by primary system organ class and preferred term.
- by primary system organ class, preferred term and maximum severity.

Separate summaries will be provided for study medication related AEs, death, SAEs, other significant AEs leading to discontinuation.

The number and percentage of participants with AEs of special interest (AESI) will be summarized. AESI will be defined based on the latest Case Retrieval Strategy.

A participant with multiple AEs within a primary system organ class is only counted once towards the total of the primary system organ class.

Vital signs

All vital signs data will be listed by participant, and visit and if ranges are available, abnormalities (and relevant orthostatic changes) will be flagged. Summary statistics will be provided by scheduled visit.

ECG

All ECG data will be listed by participant and visit, abnormalities will be flagged. Summary statistics will be provided by scheduled visit.

Clinical laboratory evaluations

All laboratory data will be listed by participant and visit and if normal ranges are available abnormalities will be flagged. Summary statistics will be provided by scheduled visit. Shift tables using the low/normal/high/ (low and high) classification will be used to compare baseline to the worst on-treatment value.

Immunogenicity

All immunogenicity results will be listed by participant and visit.

12.5.4 Pharmacokinetics

Pharmacokinetic parameters will be listed by participant and visit. Descriptive summary statistics will include mean (arithmetic and geometric), SD, CV (arithmetic and geometric), median, minimum, and maximum for the FAS.

12.6 Analysis of exploratory endpoints

12.6.1 CCI

A large, stylized red logo consisting of the letters 'CCI' in a bold, sans-serif font. The logo is positioned on the left side of a solid black rectangular background that spans the width of the page.

CCI

12.6.2 CCI

CCI

12.6.3 CCI

CCI

12.7 Interim analyses

Two interim analyses will be performed after all participants have completed Week 28 to support the registration dossier, and Week 48 to supplement the dossier with long-term safety and efficacy data. At the interim analysis at Week 28, the primary efficacy analysis will be conducted based on the data up to the time when the first 11 participants have reached Week 28 (or prematurely discontinued prior to Week 28), as per PMDA feedback received in Feb 2023. A final analysis will be performed after all participants have completed the study.

12.8 Sample size calculation

12.8.1 Primary endpoint(s)

CCI

13 Ethical considerations and administrative procedures

13.1 Regulatory and ethical compliance

This clinical study was designed and shall be implemented, executed and reported in accordance with the ICH Harmonized Tripartite Guidelines for GCP, with applicable local regulations (including European Directive 2001/20/EC, US CFR 21), and with the ethical principles laid down in the Declaration of Helsinki.

13.2 Responsibilities of the investigator and IRB/IEC

Before initiating a trial, the investigator/institution must obtain approval/favorable opinion from the IRB/IEC for the trial protocol, written informed consent form, consent form updates, participant recruitment procedures (e.g., advertisements) and any other written information to be provided to participants. Prior to study start, the investigator is required to sign a protocol signature page confirming his/her agreement to conduct the study in accordance with these documents and all of the instructions and procedures found in this protocol and to give access to all relevant data and records to Novartis monitors, auditors, Novartis Quality Assurance representatives, designated agents of Novartis, IRBs/IECs, and regulatory authorities as required. If an inspection of the clinical site is requested by a regulatory authority, the investigator must inform Novartis immediately that this request has been made.

13.3 Publication of study protocol and results

The protocol will be registered in a publicly accessible database such as clinicaltrials.gov and as required in EudraCT. In addition, after study completion (defined as last participant last visit) and finalization of the study report the results of this trial will be submitted for publication and posted in a publicly accessible database of clinical trial results, such as the Novartis clinical trial results website and all required Health Authority websites (e.g., Clinicaltrials.gov, EudraCT etc.).

For details on the Novartis publication policy including authorship criteria, please refer to the Novartis publication policy training materials that were provided to you at the trial investigator meetings.

13.4 Quality Control and Quality Assurance

Novartis maintains a robust Quality Management System (QMS) that includes all activities involved in quality assurance and quality control, to ensure compliance with written Standard Operating Procedures as well as applicable global/local GCP regulations and ICH Guidelines.

Audits of investigator sites, vendors, and Novartis systems are performed by auditors, independent from those involved in conducting, monitoring or performing quality control of the clinical trial. The clinical audit process uses a knowledge/risk based approach.

Audits are conducted to assess GCP compliance with global and local regulatory requirements, protocols and internal SOPs, and are performed according to written Novartis processes.

14 Protocol adherence

This protocol defines the study objectives, the study procedures and the data to be collected on study participants. Additional assessments required to ensure safety of participants should be administered as deemed necessary on a case by case basis. Under no circumstances including incidental collection is an investigator allowed to collect additional data or conduct any additional procedures for any purpose involving any investigational drugs under the protocol, other than the purpose of the study. If despite this interdiction prohibition, data, information, observation would be incidentally collected, the investigator shall immediately disclose it to Novartis and not use it for any purpose other than the study, except for the appropriate monitoring on study participants.

Investigators ascertain they will apply due diligence to avoid protocol deviations. If an investigator feels a protocol deviation would improve the conduct of the study this must be considered a protocol amendment, and unless such an amendment is agreed upon by Novartis and approved by the IRB/IEC and Health Authorities, where required, it cannot be implemented.

16.1 Appendix 1: Clinically notable laboratory values and vital signs

The following defined notable laboratory or vital sign abnormalities, except creatinine clearance, will be communicated at the same time as they are sent to investigators to Novartis. Novartis will determine if further consultations with Investigator(s) are appropriate.

Newly occurring selected notable laboratory abnormalities :

- Albumin: < LLN
- >3x-, 5x-, 8x-, and 10x-ULN elevations of AST, ALT, and either ALT or AST*
- Any elevations of bilirubin > ULN; elevated bilirubin to >1.5xULN, and to >2xULN*
- Any elevations of ALP >1.5xULN, >2xULN, >3xULN*
- Elevation of AST and/or ALT (>3xULN, >5x-, >10x) accompanied by elevated bilirubin (>2xULN)*
- ALT or AST >3x ULN and TBL >2x-, and ALP <2xULN
- ALP >3xULN and TBL >2xULN
- Gamma-Glutamyltransferase (GGT): > 3 x ULN
- Creatinine (serum): $\geq 1.5 \times$ ULN
- Creatinine clearance (Cockcroft-Gault formula): $\geq 25\%$ decrease from baseline
- Creatinine clearance (Cockcroft-Gault formula): $\geq 25\%$ decrease from average baseline in two consecutive visits that are ≥ 14 days apart
- Potassium: ≥ 5.5 mmol/L, or ≤ 3.0 mmol/L
- Magnesium: ≥ 1.5 mmol/L, or ≤ 0.5 mmol/L
- Sodium: ≥ 150 mmol/L, or ≤ 130 mmol/L
- Calcium: $\geq 1.2 \times$ ULN or < Lower Limit of Normal (LLN)
- Hemoglobin: ≥ 2 g/dL decrease from baseline, or < 10.0 g/dL
- Platelet count: < LLN
- White blood cell count: $\leq 0.8 \times$ LLN or $\geq 1.2 \times$ ULN
- Neutrophils: $\leq 0.9 \times$ LLN or $\geq 1.2 \times$ ULN
- Eosinophils: $\geq 1.1 \times$ ULN
- Lymphocytes: < LLN or $\geq 1.1 \times$ ULN
- Protein urine dipstick: $\geq ++$

Newly occurring selected notable vital signs abnormalities in adult patients :

- Systolic/Diastolic blood pressure: $\geq 25\%$ decrease or $\geq 25\%$ increase from baseline or to $\geq 140/90$.
- Pulse: ≥ 110 bpm with $\geq 15\%$ change from baseline, or < 50 bpm with $\geq 15\%$ change from baseline

* FDA Guidance for Industry Drug-Induced Liver Injury: Premarketing Clinical Evaluation

Note: Only post-baseline values will be flagged as notable abnormalities

Cockcroft-Gault formula (Men): $\text{CrCl (mL/min)} = [((140 - \text{age (years)}) \times \text{weight (kg)}) / (\text{serum creatinine}(\mu\text{mol/L}) / 88.4) (\text{mg/dL}) \times 72]$

Cockcroft-Gault formula (Women): $\text{CrCl (mL/min)} = [((140 - \text{age (years)}) \times \text{weight (kg)}) / (\text{serum creatinine}(\mu\text{mol/L}) / 88.4) (\text{mg/dL}) \times 72] \times 0.85$

16.2 Appendix 2: Liver event and laboratory trigger definitions & follow-up requirements

Table 16-1 Liver event and laboratory trigger definitions

	Definition/ threshold
Liver laboratory triggers If ALT, AST and total bilirubin normal at baseline:	
 • ALT or AST > 5 × ULN • ALP > 2 × ULN (in the absence of known bone pathology) • Total bilirubin > 3 × ULN (in the absence of known Gilbert syndrome) • ALT or AST > 3 × ULN and INR > 1.5 • Potential Hy's Law cases (defined as ALT or AST > 3 × ULN and Total bilirubin > 2 × ULN [mainly conjugated fraction] without notable increase in ALP to > 2 × ULN) • Any clinical event of jaundice (or equivalent term) • ALT or AST > 3 × ULN accompanied by (general) malaise, fatigue, abdominal pain, nausea, or vomiting, or rash with eosinophilia • Any AE potentially indicative of a liver toxicity
If ALT or AST abnormal at baseline:	
 • ALT or AST > 3x baseline or > 300 U/L (whichever occurs first)

Table 16-2 Follow up requirements for liver laboratory triggers – ALT, AST, TBL

ALT	TBL	Liver Symptoms	Action
ALT increase without bilirubin increase:			
If normal at baseline: ALT > 3 x ULN	Normal	None	
● No change to study treatment● Measure ALT, AST, ALP, GGT, TBIL, INR, albumin, CK, and GLDH in 48-72 hours.● Follow-up for symptoms.
If elevated at baseline: ALT > 2 x baseline or > 300 U/L (whichever occurs first)	For participants with Gilbert's syndrome: No change in baseline TBL		
If normal at baseline: ALT > 5 x ULN for more than two weeks	Normal	None	
● Interrupt study drug● Measure ALT, AST, ALP, GGT, TBIL, INR, albumin, CK, and GLDH in 48-72 hours.● Follow-up for symptoms.● Initiate close monitoring and workup for competing etiologies.● Study drug can be restarted only if another etiology is identified and liver enzymes return to baseline.
If elevated at baseline: ALT > 3 x baseline or > 300 U/L (whichever occurs first) for more than two weeks	For participants with Gilbert's syndrome: No change in baseline TBL		
If normal at baseline: ALT > 8 x ULN	Normal	None	
ALT increase with bilirubin increase:			
If normal at baseline: ALT > 3 x ULN	TBL > 2 x ULN (or INR > 1.5)	None	
If elevated at baseline: ALT > 2 x baseline or > 300 U/L (whichever occurs first)	For participants with Gilbert's syndrome: Doubling of direct bilirubin		
If normal at baseline: ALT > 3 x ULN	Normal or elevated	Severe fatigue, nausea, vomiting, right upper quadrant pain	
If elevated at baseline: ALT > 2 x baseline or > 300 U/L (whichever occurs first)			

Table 16-3 Follow up requirements for liver laboratory triggers – Isolated hyperbilirubinemia

Criteria	Actions required	Follow-up monitoring
Total Bilirubin (isolated)		
>1.5 – 3.0 ULN	
 • Maintain treatment • Repeat LFTs within 48-72 hours 	Monitor LFTs weekly until resolution to ≤ Grade 1 or to baseline
> 3 - 10 × ULN (in the absence of known Gilbert syndrome)	
 • Interrupt treatment • Repeat LFT within 48-72 hours • Hospitalize if clinically appropriate • Establish causality • Record the AE and contributing factors (e.g. conmeds, med hx, lab) in the appropriate CRF 	Monitor LFTs weekly until resolution to ≤ Grade 1 or to baseline (ALT, AST, total bilirubin, Alb, PT/INR, ALP and GGT) Test for hemolysis (e.g. reticulocytes, haptoglobin, unconjugated [indirect] bilirubin)
> 10 x ULN	
 • Discontinue the study treatment immediately • Hospitalize the participant • Establish causality • Record the AE and contributing factors(e.g. conmeds, med hx, lab)in the appropriate CRF 	ALT, AST, total bilirubin, Alb, PT/INR, ALP and GGT until resolution (frequency at investigator discretion)
Any AE potentially indicative of a liver toxicity	
 • Consider study treatment interruption or discontinuation • Hospitalization if clinically appropriate • Establish causality • Record the AE and contributing factors(e.g., conmeds, med hx, lab)in the appropriate CRF 	Investigator discretion

Based on investigator's discretion investigation(s) for contributing factors for the liver event can include: Serology tests, imaging and pathology assessments, hepatologist's consultancy; obtaining more detailed history of symptoms and prior or concurrent diseases, history of concomitant drug use, exclusion of underlying liver disease.

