6. With underlying metabolic, renal, hepatic, infectious or gastrointestinal conditions which in the opinion of the investigator compromises the participant and/ or places the participant at unacceptable risk for participation in an immunomodulatory therapy.
7. Clinical evidence of liver disease or liver injury as indicated by abnormal liver function tests at screening such as Aspartate Aminotransferase (AST), Alanine Aminotransferase (ALT), Gamma-glutamyl transferase (GGT), alkaline phosphatase (ALP)(must not exceed 3 times the upper limit value of the normal range for age), or serum bilirubin (must not exceed twice the upper limit value of the normal range for age). Exception: participants who exceed this limit after initiating latent TB treatment may be eligible for participation in this study pending confirmation with Novartis.
8. Presence of moderate to severe impaired renal function as indicated by clinically significantly abnormal creatinine ($\geq 1.5 \times$ upper normal limit ULN) or abnormal urinary constituents (e.g., albuminuria) at screening. Evidence of urinary obstruction or difficulty in voiding at screening.
9. Use of concomitant treatments including disease-modifying and/or immunosuppressive drugs with the exception of:
 - Stable daily dose of systemic corticosteroid treatment ≥ 10 mg AND ≤ 1.0 mg/kg/day (maximum 60 mg/day) of oral prednisone (or equivalent) for at least 1 week prior to baseline
 - Stable dose of no more than one non-steroidal anti-inflammatory drug (NSAID) for at least 1 week prior to the baseline visit
 - Stable dose of methotrexate (maximum of 20 mg/m²/week) for at least 4 weeks prior to the baseline visit, and folic/folinic acid supplementation (according to standard medical practice of the center)
10. Use of following therapies:
 - Anakinra within 24 hours prior to baseline visit
 - Rilonacept within 1 week prior to baseline visit
 - Tocilizumab within 3 weeks prior baseline
 - Etanercept within 4 weeks prior baseline
 - Infliximab within 12 weeks prior to the baseline visit
 - Golimumab within 12 weeks prior to the baseline visit
 - Adalimumab within 8 weeks prior to the baseline visit
 - Abatacept within 10 weeks prior to the baseline visit
 - Rituximab within 26 weeks prior to the baseline visit

- Leflunomide within 4 weeks prior to the baseline visit. Documentation of a completion of a full cholestyramine elimination treatment after most recent leflunomide use will be required.

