10.2 Additional Safety Monitoring

10.2.1 Liver safety monitoring

To ensure participant safety and enhance reliability in determining the hepatotoxic potential of an investigational drug, a standardized process for identification, monitoring and evaluation of liver events has to be followed.

Please refer to [Table 16-1](#) in [Section 16.2](#) for complete definitions of liver laboratory triggers.

Once a participant is exposed to study treatment, every liver event defined in [Table 16-1](#) should be followed up by the investigator or designated personnel at the trial site, as summarized below. Additional details on actions required in case of liver events are outlined in [Table 16-2](#).

- Repeat liver chemistry tests (i.e., ALT, AST, TBL, PT/INR, ALP and G-GT) to confirm elevation. These liver chemistry repeats will be performed using the central laboratory. If results will not be available from the central laboratory, then the repeats can also be performed at a local laboratory to monitor the safety of the participant. If a liver event is subsequently reported, any local liver chemistry tests previously conducted that are associated with this event should have results recorded on the appropriate CRF. If the

initial elevation is confirmed, close observation of the participant will be initiated, including consideration of treatment interruption if deemed appropriate.

- Discontinuation of the investigational drug (refer to the Discontinuation of study treatment section), if appropriate
- Hospitalization of the participant if appropriate
- Causality assessment of the liver event
- Thorough follow-up of the liver event should include
- These investigations can include based on investigator's discretion: serology tests, imaging and pathology assessments, hepatologist's consultancy; obtaining more detailed history of symptoms and prior or concurrent diseases, history of concomitant drug use, exclusion of underlying liver disease

All follow-up information and procedures performed must be recorded as appropriate in the CRF.

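### For participants with abnormal liver values at baseline, the liver-event definition in Protocol Table 16-1 does not match the action rows in Table 16-2

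*Protocol*

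**What the plan says.** Protocol Section 10.2.1 makes Table 16-1 the definition: "every liver event defined in [Table 16-1](#) should be followed up by the investigator or designated personnel". It then refers to Table 16-2 for further detail on actions, and that table is titled "Follow up requirements for liver laboratory triggers – ALT, AST, TBL".

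Table 16-1 has two baseline categories.

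- The first is headed "If ALT, AST and total bilirubin normal at baseline". Under it stand the isolated ALT/AST, ALP and bilirubin limits, the transaminase-plus-INR trigger, the potential Hy's Law trigger, jaundice, the transaminase-plus-symptoms trigger, and adverse events suggesting liver toxicity.
- The second is for abnormal ALT or AST at baseline. It holds a single trigger: "ALT or AST > 3x baseline or > 300 U/L (whichever occurs first").

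Table 16-2 uses a different starting level for the second group: "If elevated at baseline: ALT > 2 x baseline or > 300 U/L (whichever occurs first"). That level appears alone, combined with bilirubin above twice ULN or INR above 1.5, and combined with symptoms.

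Table 8-2 says that PT/INR and GLDH are measured when there is a liver event, and points back to Section 10.2.1. Exclusion criterion 7 admits participants with raised enzymes at screening: the values "must not exceed 3 times the upper limit value of the normal range for age". Bilirubin may be up to twice ULN, and there is an exception to these limits after the start of latent TB treatment.

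**The concern.** The definition decides who enters liver-event follow-up, and the action table is meant to say what happens next. If an action row describes values that the definition does not count as an event, a site cannot tell from the text whether Section 10.2.1 applies.

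The affected group is not remote in this disease. Liver enzyme abnormality is a minor Yamaguchi criterion (Protocol Section 5.1 and Appendix 3), ALT or AST up to 3 times ULN is eligible, and SAP 2.8.1.1 lists drug-induced liver injury as a safety topic. At stake are which cases receive the Section 10.2.1 work-up, which have PT/INR and GLDH measured, and whether liver events are recorded consistently across baseline groups.

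**Working it through.** **Inputs.** Baseline ALT is b times ULN, up to the ceiling of 3 at screening (exclusion criterion 7). The triggers for abnormal or elevated baseline come from Tables 16-1 and 16-2. The documents give no ULN for ALT, so I assume 40 U/L and show 30 and 45 U/L as a range. The ULN affects only the 300 U/L limb.

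**Formulas, in multiples of ULN.**

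- Table 16-1, abnormal baseline: ALT above min(3b, 300/ULN).
- Table 16-2, elevated baseline with bilirubin, INR or symptoms: ALT above min(2b, 300/ULN).

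An ALT above the second limit but not above the first, with the accompanying finding, has a row in the action table and is not a defined liver event.

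**Example (ULN 40 U/L).** Baseline ALT is 60 U/L (60/40 = 1.5 × ULN), on-study ALT is 150 U/L, and bilirubin is 2.5 × ULN. AST is assumed not to meet the Table 16-1 trigger itself.

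- Table 16-2 combined row: 2 × 60 = 120. Since 150 > 120 and 2.5 > 2, the row is met.
- Table 16-1: 3 × 60 = 180. Since 150 < 180 and 150 < 300, there is no event.
- Ratios: 150/60 = 2.5 × baseline, and 150/40 = 3.75 × ULN.

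**Range of baselines (all entries × ULN).** The 300 U/L limb equals 10.00, 7.50 and 6.67 × ULN for a ULN of 30, 40 and 45 U/L.

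| Baseline ALT | Table 16-2 combined row above | Table 16-1 above, ULN 30 | ULN 40 | ULN 45 |
|---|---|---|---|---|
| 1.25 | 2.50 | 3.75 | 3.75 | 3.75 |
| 1.5 | 3.00 | 4.50 | 4.50 | 4.50 |
| 2.0 | 4.00 | 6.00 | 6.00 | 6.00 |
| 2.5 | 5.00 | 7.50 | 7.50 | 6.67 |
| 3.0 | 6.00 | 9.00 | 7.50 | 6.67 |

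The mismatch exists at every raised baseline shown. At ULN 40 its width runs from 1.25 × ULN (baseline 1.25) to 2.5 × ULN (baseline 2.5). Over all the entries it runs from 0.67 (6.67 − 6.00) to 3.00 (9.00 − 6.00).

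**Related gaps, from the passages side by side.**

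- Raised bilirubin with normal ALT and AST at baseline fits neither Table 16-1 category. The first requires all three to be normal, and the second requires ALT or AST to be abnormal.
- The Table 16-2 row "If normal at baseline: ALT > 8 x ULN" has no counterpart for elevated baseline, and the text does not say whether that is intended.
- Table 16-1 triggers on ALT or AST, while the transaminase column of Table 16-2 is ALT only.

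**The case against.** The strongest reply is that nothing is lost in practice. Table 16-2 keeps elevated-baseline rows for bilirubin or INR and for symptoms. Table 16-3 has bilirubin rows and a general liver-adverse-event row that do not depend on baseline ALT or AST. Appendix 1 and SAP 5.4 flag newly occurring ALT or AST above 3 × ULN with bilirubin above 2 × ULN, and the example meets that. Section 6.6 allows interruption for a significant safety risk. This stands to the extent that such a value would be seen. It does not close the mismatch. Appendix 1 leaves the sponsor to decide on consultation with the investigator and states no site action. It lists no combination with INR or symptoms, and none of these provisions makes the value a liver event.

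Three stronger readings are tempting, and the documents do not support them.

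- A reader might infer that the protocol defines liver events twice, or that Hy's Law cases go undetected. Table 16-2 sets follow-up and does not define events. The example gives neither ALP nor the conjugated fraction, so its Hy's Law status is not established.
- With a baseline of 100 U/L, an ALT of 195 U/L with raised bilirubin reaches neither table's ALT limit (2 × 100 = 200). That is a threshold on which the tables agree, so it is not a contradiction. Preferring another limit is a clinical judgement.
- The Section 10.2.1 wording on close observation, "including consideration of treatment interruption if deemed appropriate", might seem to conflict with rows that state interruption. It belongs to a summary that refers to Table 16-2 for detail. Likewise, a monitoring tier for isolated ALT between 3 and 5 × ULN at normal baseline is ordinary staging.

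The layout is also a fair caution. The action cells for the combined rows are blank in the extracted text, so I rely on the rows existing and not on any particular action. Jaundice and liver adverse events are not laboratory items, so a row boundary in Table 16-1 may have been lost.

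**Conclusion.** The point holds as a mismatch between definition and action for participants with abnormal baseline values. On the text as read, values between the two limits have a row in Table 16-2, are not Table 16-1 events, and so do not by definition trigger Section 10.2.1 or the liver-event tests in Table 8-2. The existence of the gap does not depend on the assumed ULN; only its upper edge at high baselines does.

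The conclusion rests on the extracted grouping in Table 16-1. If the original page shows the combined triggers applying to every baseline, most of the point falls away.

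The practical size is modest. SAP 2.5.6 counts 14 participants, enrollment has stopped, and the documents do not say how many entered with raised enzymes. Treatment is open-ended, however, so the rules continue to operate. The primary efficacy analysis is unaffected. This should be corrected because it concerns safety follow-up and costs little.

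**What to change.** The sponsor should check Table 16-1 against the source layout. It should then reconcile Section 10.2.1, Table 8-2, Table 16-1 and Table 16-2 so that the liver-event definition and the action rows agree for each baseline category: all normal, raised ALT or AST, and raised bilirubin alone. The text should also say how AST-only events relate to the ALT-based rows, and whether the absence of an elevated-baseline counterpart to the 8 × ULN row is intended. All thresholds and actions are for the sponsor to decide; none is proposed here.

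The cost is a protocol amendment to the appendix tables and a few sentences. Depending on how the tables are aligned, there may be a few more liver-event records and the PT/INR and GLDH tests that go with them.
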